#### **1.0 Specific Aims**

The coronavirus disease 2019 (COVID-19) global pandemic rapidly changed the standard model of prenatal care in the United States. In response to this pandemic, the Society for Maternal Fetal Medicine (SMFM) and the American College of Obstetricians and Gynecologists (ACOG) recommended integrating telehealth services as appropriate, limiting face-to-face patient contact if clinically possible, and considering alternative methods of providing obstetric care, to decrease the risk of COVID-19 exposure.

Evidence for integrating home monitoring devices and telehealth services for the provision of prenatal care is limited Innovative options for home monitoring of fetal well-being, as a component of virtual or a hybrid prenatal care model is equally negligible. While a few studies have focused on home monitoring of maternal blood pressure, capillary blood glucose, and contraction patterns, few have investigated maternal home monitoring of fetal heart rate, as a component of virtual or hybrid prenatal care.

In addressing this gap, HeraMED designed and tested a medical grade, smartphone fetal heart rate monitor - HeraBEAT USATM ((HeraBEATTM) - for self-administration at home, under clinical guidance of an obstetric provider.

We propose that HeraBEATTM self-administered at home by pregnant women, under clinical guidance, will result in accurate monitoring of fetal heart rate, provide peace of mind to patients between prenatal appointments, and enhance the overall prenatal experience of pregnant women.

To evaluate the functionality and acceptability of HeraBEATTM we plan to:

- 1. Assess the functionality of HeraBEAT™ self-administered by pregnant women.
  - a. Hypothesis: Pregnant women will demonstrate a working knowledge on use of the device, when observed by medical staff, will trouble-shoot appropriately and will rate the device instructions as easy to follow.
  - b. Hypothesis: Pregnant women will appropriately self-monitor FHR successfully at home, transmit the data to caregivers, and use the device as prescribed.
- 2. Assess the acceptability of HeraBEATTM when self-administered by a pregnant women in the home by assessing the following
  - a. Hypothesis: Pregnant women will rate the device as easy to use, easy to interpret, and have minimal disruption in lifestyle as measured by a standardized survey.
  - b. Hypothesis: The intervention will reduce the rate of healthcare utilization without impacting maternal safety or the process of care standards specified by the American College of Obstetricians and Gynecologists (ACOG).

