## 5.6 Schema

Patients will be instructed to monitor their fetus once weekly, using their assigned device, from 20 weeks to 36/37 weeks gestation. Patients using the HeraBEATTM device will have their FHR and MHR data displayed on their App, and uploaded to a HIPPA compliant cloud based server, which can be accessed by the healthcare provider for review (*Appendix B*). Patients using the standard handheld Doppler device will be given a study brochure for recording their weekly data. Patients using the HeraBEATTM device will be instructed to bring their device during their outpatient clinical appointments, for comparison of MHR and FHR during their routine clinic appointments using methods documented in *Appendix E*.

After approximately 8 weeks of monitoring, patients will complete a System Usability Survey (SUS Survey), *Appendix D* to assess ease of use of the device, then crossover to the alternate study product.

Patients who are randomized to HeraBEATTM from 20weeks gestation to 28 weeks gestation will be given the standard fetal Doppler. Patients who are randomized to the standard Fetal Doppler will switch to the HeraBEAT.TM At the conclusion of each patient device use (28 weeks and 36 weeks gestation), participants will complete the System Usability Survey (Appendix D) to assess ease of use of each device.

- 1- Nurse assesses eligibility criteria, ascertains mother's interest, and study coordinator will obtain consent and complete randomization Patients will be given home monitoring equipment after their fetal anatomy sonography is complete, inclusion/exclusion criteria confirmed and Patient Usability Form completed (Appendix C).
- 2- After 8 weeks of use, participants will complete the System Usability Scale (SUS) survey (Appendix D), return the first study device and crossover to the second device. An independent device use assessment (Appendix C) will be assessed by study nursing staff and completed for the second device.
- 3- At the conclusion of 8 weeks of self-monitoring with assigned device, participants will complete the System Usability Scale (SUS) survey to assess ease of use (Appendix D).

Prior to registering study participants, all eligibility criteria will have been met and fully documented. Mothers will be randomized by the study coordinator after completion of standard informed consent for participation in clinical research including permission to use Protected Health information.

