#### 8.0 Data Analysis Plan

The study will be analyzed according to the intention to treat principle, including all mothers randomized to the study in the arm to which they were randomized, regardless of whether they received the intervention assigned.

Baseline characteristics will be reported in the study results with continuous values being reported as means and standard deviations or median interquartile range as appropriate. Categorical values will be reported as counts and proportion. Two sample t-tests or Wilcoxonrank sum test and chi-squared tests or Fishers exact test will be used as appropriate. Any baseline imbalances (p<0.05) will be explored as a possible confounder to adjust for when the outcome measures are analyzed. We will adhere to the CONSORT guidelines to transparently

report study results and ensure that sufficient information is included to allow for assessment of the study's internal and external validity.

Ease of use will be estimated from the System Usability (SUS) validated questionnaire. These data will be analyzed as a two sample t-test prior to cross over. After cross over we will analyze these data using an ANCOVA adjusting for order of medical devices or as a paired t-test as appropriate.

Within the SUS survey, we will also examine trends within individual questions using chi-square tests. Clinical concerns in FHR will be indicated as a FHR less than 110 bpm or greater than 160 bpm. These data will be analyzed as McNemar's test on the association of the study medical devices with the clinical standard of care. Comparing ease of use metrics will be done using an ANCOVA analysis or generalized estimating equation as appropriate adjusting for gestational age. Additional ad-hoc analysis will be performed using standard techniques appropriate for randomized trials, with each outcome compared between study arms using t-tests for continuous outcomes and chi-square tests for dichotomous outcomes. If there are differences in baseline characteristics between the two study groups, these will be accounted for using ANCOVA or regression models which include an indicator for study arm.

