## 8.2 Sample Size

Difference in ease of use between our standard fetal Doppler and HeraBEAT™ device, as measured by the System Usability Survey (SUS) will be the primary outcome. Approximately 1500 – 2000 expectant mothers receive prenatal care in the obstetric department annually. We aim to recruit 50 participants (50 per arm, with cross-over) for a 99.7% power to detect a 10-point difference in SUS, as this accounts for a withdraw / post-randomization exclusion, estimated as high as 10% (assuming a proportion of expectant mothers to withdraw participation after being enrolled or found to not meet criteria after the fact).

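### Hypothesis 2b names no comparator and no margin: the design can give an imprecise HeraBEAT-versus-Doppler contrast in urgent visits, but not a reduction against unmonitored care or a finding of no impact

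*Combined protocol and SAP*

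**What the plan says.** Section 1.0 (hypothesis 2b) reads: "The intervention will reduce the rate of healthcare utilization without impacting maternal safety", and it extends the no-impact claim to the process-of-care standards set by ACOG. It does not say what the intervention is compared with, or how large a change in safety or process of care would count as an impact.

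The comparator device is a standard fetal Doppler, also supplied for home use (Section 5.5). Section 5.6 states: "Patients will be instructed to monitor their fetus once weekly, using their assigned device, from 20 weeks to 36/37 weeks gestation". All women change device after about 8 weeks. Section 5.7 keeps tests and evaluations the same in both arms.

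The secondary objective in Section 5.1 is neutral in direction: the impact on urgent triage or emergency visits for fetal well-being concerns. Section 5.9.3 lists clinic visits, triage visits and hospitalisations, with a qualifier about home readings having prompted them. That qualifier may apply to the hospitalisations only or to the whole list. Section 5.8 collects utilisation, delivery and safety data up to the visit 6 to 8 weeks after birth.

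Section 8.0 analyses women by intention to treat in the arm to which they were randomised. It names methods for SUS, ease of use and FHR flags. Anything else falls under ad hoc analysis, with "each outcome compared between study arms using t-tests for continuous outcomes and chi-square tests for dichotomous outcomes". Section 8.2 makes the SUS difference the primary outcome and bases the 50 women on it alone.

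**The concern.** Hypothesis 2b joins a directional claim (utilisation falls) to two no-effect claims (safety, process of care). The background in Sections 1.0 and 2.0 is about limiting face-to-face contact and redesigning prenatal care, so a reader will naturally take the reduction as being against usual care. No woman and no period in this trial supplies that comparison.

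On the narrower reading, HeraBEAT against Doppler, the randomisation helps, but the only analysis rule available for visits can cancel the device effect. A no-effect statement also needs a margin, and none is given. The stake is a secondary conclusion on utilisation or safety that the data could not support.

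**Working it through.** **The plan's own figure.** Section 8.2 reads "We aim to recruit 50 participants (50 per arm, with cross-over"), "for a 99.7% power to detect a 10-point difference in SUS", allowing for "withdraw / post-randomization exclusion, estimated as high as 10" per cent. This is 50 women in total, and 50 × 0.9 = 45 if the full loss occurs. SD, alpha and within-woman correlation are not stated. Assuming a paired analysis and two-sided alpha 0.05, the SD of differences that gives 99.7% power is 10√n / (1.960 + 2.748): 14.2 for n = 45 and 15.0 for n = 50. The figure is attainable but cannot be confirmed from the documents. It concerns SUS only and gives no support to 2b.

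**Comparison with no home monitoring.** Unmonitored women: 0. Unmonitored periods: 0. The effect is not estimable at any sample size.

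**Comparison of sequences over the whole follow-up.** Let μ be the weekly visit rate, π₁ and π₂ the period effects, δ the HeraBEAT effect, and F the visits after both periods. Assume no carryover.
- HeraBEAT first: 8(μ + π₁ + δ) + 8(μ + π₂) + F
- Doppler first: 8(μ + π₁) + 8(μ + π₂ + δ) + F
- Difference: 8δ − 8δ = 0

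If the device instead multiplies the rate by θ, with period rates λ₁ and λ₂ on Doppler, the difference is 8(λ₁ − λ₂)(θ − 1). This is zero when the period rates are equal. Otherwise its sign depends on which period is busier, so it is still not the device effect.

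**Comparison of devices within women.** The documents give no visit rates, so those below are assumptions. Calculations use 45 women and two-sided 0.05. Let p₁ and p₂ be the proportions of women with a visit in the Doppler and HeraBEAT periods. With independent periods, the discordant probabilities are p₁(1 − p₂) and p₂(1 − p₁). Exact McNemar power to show a halving:

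| Doppler → HeraBEAT | Independent periods | Within-woman correlation 0.3 |
|---|---|---|
| 10% → 5% | 6% | 5% |
| 20% → 10% | 17% | 22% |
| 30% → 15% | 31% | 40% |
| 50% → 25% | 60% | 77% |

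For visit counts (Poisson, exact conditional test), power to show a halving of 0.1, 0.3, 0.5 or 1.0 visits per 8 weeks is 6%, 25%, 42% or 76%.

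As an interval, take 0.3 halved to 0.15. Expected visits are 45 × 0.3 = 13.5 and 45 × 0.15 = 6.75. The SE of the log rate ratio is √(1/13.5 + 1/6.75) = 0.471. The 95% CI around 0.5 is 0.5 ÷ 2.52 to 0.5 × 2.52, or about 0.20 to 1.26.

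**Safety.** With no events in n women, the exact two-sided 95% upper limit is 1 − 0.025^(1/n):
- n = 50: 7.1%
- n = 45: 7.9%

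An event with a true rate of 2% would not be seen at all in 45 women with probability 0.98^45 = 40%.

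For scale, consider a parallel-group non-inferiority comparison with an assumed 5-point margin, one-sided 0.025 and 80% power. It needs (1.960 + 0.842)² × 2p(1 − p) / 0.05² women per arm: 124, 299 or 566 at event rates of 2%, 5% or 10%.

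**The case against.** The strongest reply is that 2b names no comparator, so the usual-care reading is the reader's inference. Section 8.0 uses the word intervention for the randomised assignment. On that reading the crossover gives a randomised HeraBEAT-versus-Doppler contrast, absent carryover, and the remaining problem is precision and analysis. This stands. A reader might infer that the design can say nothing about utilisation, and the documents do not support that.

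Second, the objective in Section 5.1 is already neutral, and SUS "as measured by the System Usability Survey (SUS) will be the primary outcome". A directional hypothesis among the aims is not a planned conclusion. This also stands and limits the weight of the point.

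Third, a reader might infer that the sponsor intends to declare safety from a non-significant test. No section says so. Adverse events are to be recorded and assessed for severity and for relationship to HeraBEAT (Section 5.7), and safety concerns go to an existing review board (Section 9.2). What remains is that the only analysis rule that could reach safety is the generic one in Section 8.0, and it has no margin.

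Fourth, the word arm is not used consistently. Section 8.0 ties it to randomisation, hence to sequence, while the bracket in Section 8.2 uses it for device. The zero contrast applies only to the sequence reading with visits pooled over both periods. The plan does not exclude that reading, and the intention-to-treat sentence favours it.

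**Conclusion.** The point holds in a limited form. A reduction against care without home monitoring is not estimable. A HeraBEAT-versus-Doppler contrast is available from the crossover, but the stated between-arm rule, applied by sequence over the whole follow-up, has an expected device contrast of about zero. That result assumes no carryover and similar visit rates in the two periods.

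A correct within-woman analysis in 45 to 50 women is likely to be imprecise. The power figures rest on assumed visit rates and would be acceptable only if visits were very common and the effect large.

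A conclusion of no impact on safety or process of care cannot be drawn without a margin. For safety, zero events would leave an upper limit of 7.1% to 7.9%. Delivery and postpartum events follow use of both devices, so they can be compared only by device order.

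If Section 5.9.3 means that all visits count only when prompted by home readings, that endpoint could not show a net reduction against unmonitored care, because such visits cannot occur without home monitoring.

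This is a defect in a secondary hypothesis and its analysis. It does not touch the primary SUS comparison.

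**What to change.** - **Hypothesis.** Restate 2b as exploratory: the rate of urgent visits for fetal well-being concern is compared between HeraBEAT and standard Doppler periods within women.
- **Endpoint.** Use the Section 5.1 definition and reconcile Section 5.9.3 to it, stating whether a visit must have been prompted by a home reading to count.
- **Analysis.** Count visits within each 8-week device period. Report a within-woman rate ratio with 95% CI, adjusted for period. Use exact methods if visits are rare. In Section 8.0, say whether arm means sequence or device.
- **Safety.** Report events descriptively by device period with exact 95% CIs. Report delivery and postpartum events overall or by sequence, without attributing them to a device.
- **Claims.** Make no claim of reduction against usual care, and no claim of no impact on safety or on the ACOG process-of-care standards.

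The cost is protocol wording, a little more analysis and a narrower secondary claim. No new arm, visits or participants are needed.

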#### 2.0 Background and Significance

The current traditional rhythm of prenatal care in the United States assumes dependence on brief face to face visits consisting of low-level physical assessments and the opportunity to communicate about the progress of the pregnancy. It has been proven that this method provides benefit to mothers and their fetuses, but the potential that greater benefit could be achieved using 21st century technology has not been widely explored. The current COVID-19 pandemic has shifted the method in which obstetric providers plan and provide prenatal care, as global practice changes encourages limited face-to-face interaction, with more reliance on telehealth options for the provision of care.

Alternative models for the provision of obstetric care is limited in the literature, but have recently gained traction in obstetric practice, given the current COVID-19 pandemic. A recent systematic review of telehealth interventions to improve obstetric care reported improved schedule optimization for high risk pregnancies, and improved obstetric outcomes for smoking cessation

and breastfeeding. Our randomized, telemedicine integrated, reduced model care – OB Nest – augmented with fetal Doppler and sphygmomanometer home monitoring devices resulted in higher patient satisfaction of care among OB Nest patients while maintaining similar maternal and fetal outcomes when compared to standard prenatal care. Similarly, a study which decreased the frequency of prenatal care and augmented care with a mobile prenatal care App, found no difference in patient or provider satisfaction.

Despite the rapid growth in a variety of technological advances and innovations in healthcare to support home monitoring, including home holter monitors, wireless scales for monitoring weight, and home sphygmomanometer for monitoring blood pressure, there has been relatively little research efforts focused on home monitoring devices, self-administered by pregnant women, under the guidance of a clinical team, especially innovative options for home monitoring of fetal well-being. This gap is important as leveraging innovative technological advances and other connected health modalities may allow future re-design of prenatal care, that enhances the overall experience of expectant mothers while allowing for rapid adoption during healthcare crises like the current global COVID-19 pandemic.

Recently, the Clinical Excellence Research Center at Stanford University proposed that the costs of delivering prenatal care could be reduced by 2.5% to 13% by using supplemental telehealth innovative tools. Despite the major impact this could potentially have on the delivery of prenatal care, research and investments in this concept has remained limited, and uptake slow, until the recent COVID-19 pandemic.

Consequently, this study proposes to assess HeraBEAT,TM a novel fetal heart rate device, administered at home by pregnant women, under clinical guidance, to augment options for virtual prenatal care.

## 3.0 Preliminary Research

## 3.1 Basic Principles of FHR Monitoring

Fetal heart rate monitoring is a method for examining the condition of an unborn fetus in the uterus by noting its heart rate. This is typically done by a manual handheld device in an outpatient setting during routine prenatal care, or continuously, by electronic FHR measurement when pregnant women are admitted for obstetric care. Fetal ultrasound is also utilized to monitor FHR in clinical settings. These methods for monitoring FHR was originally introduced in the 1960s and 1970s, with the hope that it would assist physicians in the diagnosis of fetal hypoxia or abnormal fetal heart.

# **3.2 Doppler FHR Principle**

The typical Doppler fetal heart rate monitor is a hand-held ultrasound transducer that uses the Doppler Effect to provide an audible simulation of the heart beat and displays the number of beats per minute. To achieve this, the device is pressed against a pregnant women's abdomen and acoustic waves are then interpreted as FHR. An ultrasound probe is a key component in the system. The probe consists of an oscillator to generate ultrasound frequency (for these applications, the range is 1–3 MHz) followed by an amplifier to condition the sine wave in the order of volts. This waveform is applied to the transmitter transducer to send vibrations through the body and bounce back when the density of the medium changes. Another transducer is then used to receive the bounced vibrations and convert them to electrical signals. Basic FHR Doppler systems are available for outpatient use under clinical guidance. However, self-monitoring of FHR by pregnant women at home is currently not a standard approved use of FHR Doppler devices, although Doppler devices are routinely sold for public consumption.

#### **3.3 Investigational Device**

The 'HeraBEAT USATM (HeraBEATTM) is a wireless Smart Fetal Ultrasound Doppler measuring device designed to be self-administered by pregnant women. The 'HeraBEATTM' device safety and performance claims allow continuous and accurate measurement of fetal heart rate (FHR) and maternal heart rate (MHR) throughout the pregnancy starting at 12 weeks gestation. This study shall evaluate the device performance starting at 20 weeks gestation.

Technologically, HeraBEATTM is similar to other FHR devices currently on the market in terms of device usage but differ by design in its interface. The HeraBEATTM device uses a smartphone-based interface, with real time instructions for localizing FHR. The device also measures the maternal heart rate (MHR) and uses this in its algorithm. This is primarily in order to overcome common lay person usage errors such as confusion between MHR and FHR or difficulties locating the FHR due to lack of experience. The data obtained from the device is uploaded to a secure HIPAA compliant cloud-based server for medical providers to review. The intended use, indication for use and contraindications are similar to current medical grade handheld fetal Doppler devices.

The specifications for the HeraBEATTM are:

- The device will measure fetal heart rate in range of 50-240 BPM.
- The device will measure fetal heart rate with accuracy of  $\pm 2$  BPM.
- The device will measure fetal heart rate with resolution of 1 BPM.
- FHR value is calculated and displayed every 1 second.
- Device measures FHR and MHR starting at 12 week gestation.
- The device will measure maternal heart rate in range of 45-240 BPM.
- The device will measure maternal heart rate with accuracy of  $\pm 2\%$  or 1 BPM, whichever is greater.
- The device will measure maternal heart rate with resolution of 1 BPM.

• MHR value is calculated and displayed every 1 second.

## **3.4 Device Components**

The 'HeraBEATTM' device is a handheld device consisting of two main units:

- 1. The HeraBEATTM sensor device and
- 2. The HeraBEATTM smart phone application for iOS/Android (App).

The function of the HeraBEATTM device is to sense the fetal heart rate signals, process the data and transmit the information wirelessly to the HeraBEATTM App. The HeraBEATTM App. receives the digital information from the HeraBEATTM device, displays the data to the user, saves it for additional use, controls the commencement and termination of the measurement session, and automatically sends the measurement data to a qualified HIPAA compliant cloud server(HeraBEAT dashboard).

The HeraBEATTM device (Figure 1) is a wireless device, operating on rechargeable battery (low voltage) that communicates with a smartphone via standard low power bluetooth-4 Low Energy (BLE) data link. The HeraBEATTM device does not contain buttons or switches. Power ON/OFF management is executed via timers and sensing of motion by the accelerometer. The HeraBEATTM device is managed by an internal Microcontroller (MCU). It controls the battery charger and power management, Blue Tooth Low Energy (BLE) and indicator lights.

Figure 1. Illustration- Left:  $HeraBEAT^{TM}$  app. Right:  $HeraBEAT^{TM}$  device.

